Abbreviations: AE=Adverse event, BSA = body surface area; CGIC = Clinician Global Impression of Change; CGIS = Clinician Global Impression of Severity; C-SSRS = Columbia-Suicide Severity Rating Scale; DLQI = Dermatology Life Quality Index; ECG = electrocardiogram; EoT = End of Treatment; EoS = End of Study; HBsAg = hepatitis B surface antigen; HCV = hepatitis C virus; HIV = human immunodeficiency virus; IWRS = Interactive Web Response System; mNAPSI=modified Nail Psoriasis Severity Index; NAPPA-QoL = Nail Assessment in Psoriasis and Psoriatic Arthritis Quality of Life; NAPSI = Nail Psoriasis Severity Index; NRS = Numeric Rating Scale; OSFU = Observational Safety Follow-up; PASI = Psoriasis Area and Severity Index; PGA-S = Physician Global Assessment-Skin; PGIC = Patient Global Impression of Change; PGIC-P = Patient Global Impression of Change for pain; PGIS = Patient Global Impression of Severity; PGIS-P = Patient Global Impression of Severity for pain; SC = subcutaneous; TB = tuberculosis; SC = subcutaneous; s-PGA = static Physician's Global Assessment; TB = tuberculosis; ViSENPsO= Visual Medical Scale to Evaluate Nail Psoriasis Severity; TEAE = Treatment-emergent Adverse Event

- a. Subjects who experience significant worsening of plaque psoriasis at Week 16 (defined as an increase in static Physician's Global Assessment [s-PGA] by at least 2 from the baseline measurement) will be eligible for an early escape.
- b. Subjects initially randomized to the placebo arm will begin tildrakizumab subcutaneous (SC) treatment at Week 28 for Part 2 of the study.
- c. Subjects who withdraw from the study will undergo the assessment corresponding to the last assessment of the study part from which they are leaving. Week 52 assessments (EoT) should be conducted approximately 4 weeks after administration of the last dose of study treatment.
- d. Perform a check that all inclusion/exclusion criteria remain satisfied at Baseline, including those related to results from tests performed at the Screening visit.
- e. Height and weight only.
- f. Adverse events reported prior to initiation of study treatment (Day 1) are to be recorded as non-TEAE.
- g. Chest X-ray is required only if a subject has positive or 2 indefinite QuantiFERON results.
- h. Any subject who is started on prophylactic treatment for latent TB during the Screening Period may be randomized 4 weeks after initiation of treatment without the need for rescreening.

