- i. Following completion of Baseline assessments and confirmation that all inclusion/exclusion criteria have been met.

Tildrakizumab

- j. All study procedures of Baseline should be completed prior to study treatment administration. Following randomization, study treatment administration will begin on Day 1 of Week 0, Week 4, Week 16, and Week 28. At Week 28, subjects initially randomized to placebo will be switched over to receive tildrakizumab 100 mg at Weeks 28, 32, and 44. Subjects initially randomized to tildrakizumab 100 mg will continue to receive the active drug at Weeks 28, 40, and 52. In order to maintain blind, subjects who were initially randomized to placebo will receive matching placebo injections at Weeks 40 and 52, while subjects who were initially randomized to tildrakizumab will receive matching placebo injections at Weeks 32 and 44. Study treatment will be administered after performing all study-specific procedures for a particular visit.
- k. Blood samples are to be collected (pre-SC dose where applicable), after ECG and vital signs measurements. At visits where lipids are to be assessed, the blood samples are to be collected (pre-SC dose where applicable) after at least 12 hours fasting, following ECG and vital signs measurements. The following parameters will be reported at Screening only: Serum pregnancy, hepatitis B, hepatitis C, and HIV.
- 1. Subjects with fungal nail infection whose fungal culture will be sent to the laboratory would have a Screening Period of 6 weeks.
- m. Urine pregnancy tests will be performed at the study center using materials supplied by the central laboratory.
- n. The subjects will be assessed for suicidal ideation and behavior at Screening using Screening C-SSRS, at Baseline, using Baseline C-SSRS, and each subsequent visit using the C-SSRS Since Last Visit version as specified in SoA.
- o. The efficacy assessments, ViSENPsO, NAPSI, mNAPSI, PGA-S, BSA, and PASI will be assessed at each visit during the study, starting at the Screening visit. Nail pain NRS will be based on the average score from 7-daily records at Baseline (if average of at least 4 out of the 7 daily recall observations in the week prior to baseline) and single-day recording at Screening.

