4.1.1 PART 1: Double-blind Placebo-controlled (Day 1 to Week 28)

After a Screening Period of up to 28 days and on Day 1, all eligible subjects will be randomized

1:1 to receive either tildrakizumab 100 mg or placebo administered by SC injection on Week 0 (Day 1), Week 4, and Week 16. Subjects should receive the first dose of study treatment within 24 hours of randomization. The treatment period for the double-blind, placebo-controlled part of the study is 28 weeks.

Early Escape: At Week 16, subjects who experience significant worsening of plaque psoriasis (defined as an increase in s-PGA by at least 2 from the baseline measurement) will be eligible for an early escape. (Appendix 20) Subjects selected for early escape by the Principal Investigator at Week 16 will have study medication discontinued and will complete the End of Treatment visit

assessment, followed by the observational safety follow-up period. Subjects entering early escape may be replaced so as to meet the planned evaluable sample size goal for the primary endpoint analysis.

An interim analysis may be performed that could include an unblinded sample size re-estimation (SSRE). The sample size of the study could be increased as a result of this SSRE. In the event of an increase in sample size, the total sample size of the study will not exceed a total of approximately 282 randomized subjects.

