4.1.2 PART 2: Double-blind Active Treatment Extension (Week 28 to Week 52)

At Week 28, subjects initially randomized to placebo will be switched over to receive tildrakizumab 100 mg at Weeks 28, 32, and 44. Subjects initially randomized to tildrakizumab 100 mg will continue to receive tildrakizumab at Weeks 28, 40, and 52. In order to maintain the blind, subjects in both treatment arms will receive matching placebo injections at specified time points as described in the SoA.

Subjects who experience significant worsening of plaque psoriasis at Week 28 (defined as an increase in s-PGA by, at least 2 from the baseline measurement) will be discontinued from treatment. Subjects who do not fulfill this criterion at Week 28 will continue to receive tildrakizumab in Part 2, as described above.

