4.1.3 PART 3: Observational Safety Follow-up (Week 52 to Week 72)

After Week 52 (or early termination of study treatment prior to Week 52), the study treatment should be stopped and all subjects, including those who terminated early from Part 1 and, 2 will enter the 20-week Observational Safety Follow-up period to monitor safety and tolerability for 20 weeks following the last dose of study treatment. During the follow-up period, subjects should continue on study-approved concomitant medications only, however, may be placed on appropriate therapies for safety concerns or significant worsening of psoriasis based on the judgment of the Investigator. The subjects will not receive study treatment during the follow-up period.

The study may have a primary analysis, which will be performed when the last subject has completed the Week 28 visit, and a final analysis to be performed when the last subject has completed the study.

Subjects who withdraw from the study will undergo the assessment that corresponds to the last assessment of the study part from which they are leaving. Subjects discontinued from study treatment at any time (apart from the withdrawal of informed consent) will complete the EoT (Week 52) assessment approximately 4 weeks after the last dose of study treatment and enter the 20-week observational safety follow-up. Subjects who withdraw from the study during Part 3 will undergo the Week 72 (End of Study [EoS]) assessments approximately 4 weeks after their last visit.

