6.0 STUDY TREATMENT

Study treatment is defined as any investigational treatment(s), marketed product(s), placebo, or medical device(s) intended to be administered to a subject according to the study protocol.

The study treatment in this study is tildrakizumab and placebo. All subjects will be dosed at the same time points to maintain the blind throughout the study. The study arms will receive study treatment during the course of the study as follows:

Arm A:

- o Tildrakizumab 100 mg SC injections at Weeks 0, 4, 16, 28, 40, and 52.
- Placebo injections at Weeks 32 and 44.

Arm B:

- o Placebo injections at Weeks 0, 4, 16, 40, and 52.
- o Tildrakizumab 100 mg SC injections at Weeks 28, 32, and 44.

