7.0 DISCONTINUATION OF STUDY TREATMENT AND SUBJECT DISCONTINUATION/WITHDRAWAL

7.1 Discontinuation of Study Treatment

Subjects may voluntarily discontinue study treatment for any reason at any time and enter the 20-week wash-out period or completely withdraw from the study (see Section 7.2). Subjects who consent to enter the wash-out period will undergo the Week 52 (EoT) assessment at approximately 4 weeks after administration of the last dose of study treatment.

At any time during Part 1 or Part 2 of the study, the Investigator should discontinue the study treatment of a given subject if, on balance, he/she believes that continuation would be detrimental to the subject's well-being.

The study treatment must be discontinued under the following circumstances, and the further steps need to be discussed with the Medical Monitor:

- An SAE, drug reaction or complication, or an unacceptable AE, whether attributed to study treatment or not, precludes the continuation of treatment with study treatment. This includes the development of allergic reactions or the development of other potentially serious drug reactions to medication required by the protocol.
- Diagnosis of malignancy (except basal or squamous cell carcinoma of the skin) during the study (at the discretion of the subject and Investigator).
- Meets early escape criteria at week 16 or week 28
- Subjects who develop suicidal behavior.
- Evidence of pregnancy.
- Withdrawal of informed consent.
- Lost to follow-up.
- Significant non-compliance of the subject with study procedures.
- Decision of the Sponsor to terminate the subject, study center, or the study.

Subjects who discontinue the study treatment may not be replaced.

Subjects who withdraw from the study will undergo the assessment that corresponds to the end assessment of the study part which they are leaving. Week 52 assessments (EoT) should be conducted approximately 4 weeks after administration of the last dose of study treatment.

See the SoA (see Section 1.3) for data to be collected at the time of treatment discontinuation and follow-up and for any further evaluations that need to be completed.

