After Week 52 (or early termination of study treatment prior to Week 52), the study treatment should be stopped and all subjects, including those who terminated early from Part 1 and 2 will enter the 20-week Observational Safety Follow-up period to monitor safety and tolerability for 20 weeks following the last dose of study treatment. During the follow-up period, subjects should continue on study-approved concomitant medications only, however, may be placed on appropriate therapies for safety concerns or significant worsening of

| Effective Date: 10-AUG-2020 | Page 10 of 61 |
|-----------------------------|---------------|

psoriasis based on the judgment of the Investigator. The subjects will not receive study treatment during the follow-up period.

Subjects who withdraw from the study will undergo the assessment that corresponds to the last assessment of the study part from which they are leaving. Subjects discontinued from study treatment at any time (apart from withdrawal of informed consent) will complete the EoT (Week 52) assessment approximately 4 weeks after the last dose of study treatment and enter the 20-week Observational Safety Follow-up. Subjects who withdraw from the study during Part 3 will undergo the Week 72 (End of Study [EoS]) assessments approximately 4 weeks after their last visit.

All assessments of safety in PART 3 are scheduled to happen after the date of injection at Week 52. The analysis of efficacy and safety endpoints for PART 3 will follow the analysis visit window and definitions as specified in the sections below.

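### The EoT date for an early stop can fall before the stop itself, AE collection ends on two clocks 4 weeks apart, and SAP 10.1 does not settle the Part 1 boundary for subjects with no Week 28 injection

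*Protocol*

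**What the plan says.** **EoT date.** Four places give the same interval. Protocol Section 4.1.3 applies it to every discontinuation of treatment except withdrawal of consent: such subjects "will complete the EoT (Week 52) assessment approximately 4 weeks after the last dose of study treatment and enter the 20-week observational safety follow-up". Footnote c of the Schedule of Activities says "Week 52 assessments (EoT) should be conducted approximately 4 weeks after administration of the last dose of study treatment". Protocol Section 7.1 says that subjects entering wash-out "will undergo the Week 52 (EoT) assessment at approximately 4 weeks after administration of the last dose of study treatment". SAP Section 2.1 repeats that they "will complete the EoT (Week 52) assessment approximately 4 weeks after the last dose of study treatment".

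**Stopping visits.** Early escapers at Week 16 "will have study medication discontinued and will complete the End of Treatment visit" and then move to follow-up (Section 4.1.1); no date is attached. At Week 28, Section 4.1.2 provides that subjects with "an increase in s-PGA by, at least 2 from the baseline measurement) will be discontinued from treatment". Footnote q and Section 7.1 also treat the Week 28 stop as early escape. Section 7.1 makes it a mandatory stop and refers what follows to discussion with the Medical Monitor, again without a date.

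**Dosing.** Arm A receives "Tildrakizumab 100 mg SC injections at Weeks 0, 4, 16, 28, 40, and 52". With matching placebo, both arms are injected at Weeks 0, 4, 16, 28, 32, 40, 44 and 52 (Section 6.4). Footnote j states "Study treatment will be administered after performing all study-specific procedures for a particular visit", so the s-PGA that triggers a stop is scored before that day's injection.

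**End of AE collection.** Appendix 3 ends surveillance 20 weeks from the last dose; later events are reported only if judged related. Section 4.1.3 uses the same anchor for follow-up. Section 8.3.1 counts AEs until the EoS visit is completed, after a 20-week period that follows EoT. Section 2.3 also counts from EoT.

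**AE tables.** SAP Section 10.1 describes both AE bins by onset relative to the Week 28 injection, but labels them as Day 1 to Week 28 and as Week 28 onwards. Protocol Section 9.5 has a Day 210 cut-off for subjects with no Week 28 injection. SAP Section 3.3 has a Part 3 start rule for early-terminated patients, tied to the last injection plus 28 days.

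**The concern.** Week 16 and Week 28 are both stopping visits and dosing visits, and each comes 12 weeks after the previous injection. An EoT visit counted as 4 weeks from the last dose may therefore be due well before anyone has decided to stop. A site cannot follow that, and different sites will improvise different dates.

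The EoT date also feeds the end of safety follow-up. If one passage counts 20 weeks from the last dose and another counts 20 weeks from EoT, a new AE judged unrelated and arising between the two ends is collected under one passage and not under the other. Related events stay reportable under both.

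In the tables, a bin defined by an injection that a subject never received has no closing date. AEs from off-treatment follow-up could then be counted in the placebo-controlled comparison.

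**Working it through.** All figures are nominal visit weeks.

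**Inputs.** Injections at Weeks 0, 4, 16, 28, 32, 40, 44, 52 (Protocol 6.4). EoT = last dose + 4 (4.1.3, 7.1, footnote c, SAP 2.1). AE end by Appendix 3 = last dose + 20. AE end by Section 8.3.1 = EoT + 20.

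**Completers first.** Last dose Week 52: 52 + 20 = 72. EoT at the scheduled Week 52 visit: 52 + 20 = 72. Both clocks give the protocol's Week 72.

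**Any early stop in Part 1.** After the Week 4 dose the EoT date is 4 + 4 = Week 8, and no dose is due until Week 16. After the Week 16 dose it is 16 + 4 = Week 20, and no dose is due until Week 28. A stop decided between Weeks 8 and 16, or between Weeks 20 and 28, has an EoT date already past. That is 8 + 8 = 16 of the 28 weeks.

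**The two named stops.**

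| Stop | Dose due that day | Last dose | EoT | EoT minus stop | AE end, App. 3 | AE end, 8.3.1 | Gap |
|---|---|---|---|---|---|---|---|
| Week 16 | withheld | 4 | 8 | -8 | 24 | 28 | 4 |
| Week 28 | withheld | 16 | 20 | -8 | 36 | 40 | 4 |
| Week 16 | given | 16 | 20 | +4 | 36 | 40 | 4 |
| Week 28 | given | 28 | 32 | +4 | 48 | 52 | 4 |

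Under the written EoT rule the gap is always (last dose + 4 + 20) - (last dose + 20) = 4 weeks. Section 4.1.3 carries both ends itself: it describes follow-up as 20 weeks from the last dose, yet EoT at 4 weeks plus a further 20 makes 24.

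Visit windows do not rescue the date. The 8 weeks are 56 days; a 7-day window at each end leaves 56 - 14 = 42 days.

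**AE bins.** Take a subject with no Week 28 injection and an AE at Week 32. By SAP 10.1's description the AE did not start after the Week 28 injection, so it is a Part 1 event. By the label it belongs to Week 28 onwards. To size the literal reading, assume Week w is Day 7w + 1 and use Day 210 as the reference. For a subject whose last dose was at Week 16, collection ends at Week 36 = Day 253 (Appendix 3) or Week 40 = Day 281 (8.3.1 with the written EoT rule). That leaves 253 - 210 = 43 or 281 - 210 = 71 days of later follow-up. For a last dose at Week 4, collection ends at Day 169 or Day 197, before Day 210, so nothing spills over.

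**Reach of the s-PGA rule.** Entry requires at least 3 on a 0 to 5 scale, and the rule needs a rise of 2. A baseline of 3 can reach 5; a baseline of 4 would need 6. Only subjects at exactly 3 can qualify.

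**The case against.** The strongest reply is that the past EoT date at the two named visits depends on withholding that visit's dose, which no passage states. If the dose is given, EoT falls 4 weeks after the stop and can be met. This stands as a condition on the 8-week figure. It does not dispose of the point: the same rule covers discontinuation at any time, and a stop for another reason between dosing visits meets the same difficulty.

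It can also be said that the early-escape wording is specific and overrides the general interval, and that the Week 28 stop has a route through the Medical Monitor. Both are fair. It would be wrong to infer that the Week 28 stop was left without any provision. Neither passage supplies a date, however.

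Four stronger readings are tempting and not supported:

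- **Completers are affected too**, because footnote c applied literally would move EoT past Week 52. The Schedule fixes EoT at Week 52 and EoS at Week 72, Section 4.1.3 is headed accordingly, and the interval in footnote c follows directly on a sentence about withdrawals.
- **The AE clocks differ by 12 weeks.** This needs the dose withheld and EoT held at the stopping visit, a date no passage gives.
- **The planning drop-out caps the number affected.** Subjects stopped at Week 28 attend that visit and need not be among those assumed to drop out.
- **Late AEs certainly enter the Part 1 table.** The bin labels point the other way. SAP Section 2.1 defers to visit windows and definitions elsewhere, and the rows of the visit-window table are not visible. It cannot be said that the SAP has no cut-off.

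**Conclusion.** The point holds as a reconciliation of minor severity.

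1. The written EoT interval cannot be met for a stop decided more than about 4 weeks after the last dose. At a Week 16 or Week 28 stop it gives a date 8 weeks in the past, on the assumption that the dose due that day is withheld.
2. For early stoppers, the two ends of AE collection differ by 4 weeks under the written EoT rule, whether or not the dose is given. The gap would be larger only on an assumed EoT date. Completers agree at Week 72.
3. In SAP Section 10.1, label and description disagree for subjects with no Week 28 injection. On the literal description, AEs from follow-up after Week 28 count in the placebo-controlled Part 1 table.

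Few subjects can reach the s-PGA stop, safety is analysed descriptively (SAP Section 3.5), related AEs stay reportable, and no efficacy result changes. No view is taken on which EoT timing, dosing step or follow-up length is right; the passages need to agree.

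**What to change.** In the protocol, bring Sections 2.3, 4.1.1 to 4.1.3, 7.1 and 8.3.1, footnote c of the Schedule of Activities and Appendix 3 into line, together with SAP Sections 2.1 and 3.3. They should give one EoT reference point that can be met for any early stop, and one end of AE collection. The sponsor chooses which.

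In SAP Section 10.1, state where Part 1 ends for a subject with no Week 28 injection, so that later off-treatment AEs stay out of the placebo-controlled table. The Day 210 cut-off in Protocol Section 9.5 is available for this. Because it is worded for subjects who complete Part 1, the SAP should say that it is being extended to earlier stoppers. It should also say how it fits the Part 3 start rule in SAP Section 3.3, which on one reading would begin Part 3 at about Week 20 (16 + 4) after a last injection at Week 16.

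The cost is clarifying wording in the protocol and a few sentences in the SAP. The reconciliation itself calls for no new assessments or data items.

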4.2 Scientific Rationale for Study Design

This is a randomized, double-blind, placebo-controlled, Phase 3 study to evaluate the efficacy and safety of tildrakizumab administered by SC injection in subjects with moderate to severe nail psoriasis. The study has been developed based on design features used in the completed Phase 2b protocol for subjects with psoriasis as well as ongoing Phase 3 studies for subjects with plaque psoriasis. In this study, tildrakizumab will be compared with a placebo. Placebo-controlled studies are the best way to ensure the accurate assessment (in absolute terms) of the safety and tolerability of a new molecular entity.

The study has been designed with 4 distinct phases (Screening, Double-blind Placebo-controlled period, Double-blind active treatment period, and an Observational safety follow-up period).

This enables scientific evaluation of efficacy at Week 28. The 52-week treatment duration is expected to provide adequate time to assess the safety and efficacy of tildrakizumab in subjects with nail psoriasis.

4.3 Justification for Dose

The dose of tildrakizumab was selected based on the results of Phase 2 dose-ranging study, P05495, and two Phase 3 studies (P010 and P011), in addition to an exposure-response model that was developed using these results.

In P05495, 4 treatment regimens of tildrakizumab were compared with a placebo (5, 25, 100, and 200 mg SC, administered at Weeks 0 and 4 and then every 12 weeks until Week 52). Unbalanced randomization was used to define dose-response relationships and to support the rerandomization of subjects in 2 treatment arms during the maintenance phase of the study (Part 2). At Week 16, Psoriasis Area and Severity Index (PASI) 75 response rates (primary endpoint) were 33% in the 5 mg arm, 64% in the 25 mg arm, 66% in the 100 mg arm, 74% in the 200 mg arm, and 4% in the placebo arm. The difference between each active dose versus placebo in terms of PASI 75 was statistically significant (p \leq 0.001). The proportion of subjects with PGA "clear" or "minimal" at Week 16 (key secondary endpoint) was 33% in the 5 mg arm, 58% in the 25 mg arm, 62% in the 100 mg arm, 74% in the 200 mg arm and 2% in the placebo arm. The difference between each active dose versus placebo in terms of PGA response was statistically significant (p \leq 0.001). These results demonstrated a clear dose response over the range of doses studied: the 5 and 25 mg doses demonstrated suboptimal efficacy for the PASI 75 and PGA endpoints, the 100 mg dose demonstrated near-maximal efficacy and the 200 mg dose appeared to show maximal efficacy.

The results from the Phase 2 (P05495) dose-ranging study were then used to develop an exposure-response model to analyze PASI 75 and PASI 90 response rates. The model-based analysis of the clinical data from P05495 suggested that the 100 mg dose was near the plateau of the exposure-response relationship for PASI 75. The incremental benefit for 200 mg versus 100 mg was estimated to be \sim 2% for PASI 75 response and 2% to 6% for PASI 90 response.

These findings were confirmed in two Phase 3 studies (P010 and P011) that further demonstrated that tildrakizumab 200 mg and 100 mg were efficacious and were well tolerated in the treatment of patients with moderate to severe chronic plaque psoriasis. The results for the primary and secondary endpoints in these studies were similar for tildrakizumab 200 mg and 100 mg. The results of the pivotal Phase 3 studies were the basis for the approval of tildrakizumab 100 mg in the United States on 20 March 2018 for the treatment of adults with moderate to severe plaque psoriasis who are candidates for systemic therapy or phototherapy, and in Australia on 06 September 2018 for the treatment of adults with moderate to severe plaque psoriasis who are candidates for systemic therapy.

In considering both clinical data and the model-based analysis, this Phase 3b study will include only a 100 mg dose. The safety/tolerability profile of tildrakizumab to date supports this approach.

